## 7.3 Disposition of Subjects

The number of screening failures as well as number of subjects included in this study will be described in this section. The number (n) and % (frequency distribution) of patients who were included or not in prospective phase, patients who completed the study, subjects who discontinued the study and distribution for each study dataset by IBD type will be also summarized.

## 7.4 Demographic and other characteristics

A descriptive statistical analysis will be performed for cross-sectional dataset for socio-demographic, anthropometric and clinical data: gender and age, weight, height, body mass index (BMI), professional situation, education level, income, smoking habits, medical history, comorbidities and extra intestinal manifestations, among other variables. A descriptive statistical analysis will be performed for longitudinal dataset for socio-demographic and anthropometric data, clinical and treatment-related features. Descriptive statistical analysis will be performed for each IBD type.

## 7.5 Primary Analysis

The primary endpoint analysis will be performed calculating the proportion of patients with active disease at Day 1. The results will be presented as percentage and calculated as.

- For CD:

$$p_{CD} = \frac{\# \text{ patients with active } CD (\text{HBI} \geq 8 \text{ or } \text{CDAI} > 220)}{\# \text{ total of patients with } CD} \times 100$$

- For UC:

$$p_{UC} = \frac{\# \text{ patients with active } UC (\text{Mayo partial score} \geq 5)}{\# \text{ total of patients with } UC} \times 100$$

The 95% confidence interval will be computed for each estimate. In this study, the primary endpoint will be analyzed for cross-sectional dataset.

## 7.6 Secondary Analysis

The secondary analysis include both a cross-sectional analysis and a longitudinal analysis.

The cross-sectional will be performed for cross-sectional analysis dataset:

- A descriptive statistical analysis will be performed for socio-demographic, anthropometric and clinical aspects of IBD by type (CD and UC);
- A descriptive statistical analysis will be performed for the treatment patterns for CD and UC in the previous 3 years, including the use of biologic therapies and failure to these therapies (if any), time between IBD diagnosis and initial treatment, first treatment after diagnosis of moderate to severe IBD, among other variables of interest.
- For each type of IBD (CD or UC), a comparison of patients with moderate to severe activity and patients with no or mild activity disease regarding socio-demographic, clinical and treatment variables of interest will be performed:
  - For qualitative variables, such as gender, smoking habits, professional status, family history of IBD, steroid behavior (dependent/refractory), previous treatment with biologic therapies, and previous surgery for IBD, the assessment of a significant difference between groups will be done using the Chi-Square Test or the Fisher's Exact Test depending if the assumption of cell frequency to be made;
  - For quantitative variables, such as age, time since diagnosis, and duration of treatment, such as age, time since diagnosis, and duration of treatment, the assessment of a significant difference between groups will be made through the t-test

- for independent samples or Mann-Whitney test in case of non-normality of the quantitative variable distribution;
- If applicable, for CD and UC patients, the assessment of independent variables which can be associated with disease control at day 1 will be performed using a logistic regression model. The odds ratios (ORs) estimates and the respective 95% confidence intervals will be presented.
- For each IBD (CD and UC), a descriptive statistical analysis (global and according to disease activity) for the quality of life data will be performed:
  - EuroQoL questionnaire (EQ-5D-5L) considers five attributes of quality of life evaluation:
    - Mobility;
    - Self-care;
    - Usual activity;
    - Pain/discomfort;
    - Anxiety/depression.
- Each dimension has five possible levels, 1-no problems, 2 slight problems, 3-moderate problems, 4-severe problems, 5-extreme problems.
- The resulting score of EQ-5D analog scale:
  - A value of 100 in VAS EQ-5D score indicate the best health imagined and a value of 0 means the worst health imagined;
  - Utilities will be configured such that 0.0 is associated with being dead and 1.0 is associated with perfect health; thus, a higher utility value is considered better;
- The SF-36 uses 36 items to evaluate eight health dimensions:
  - Physical functioning (raw score) – Sum of Q3a, Q3b, Q3c, Q3d, Q3e, Q3f, Q3g, Q3h, Q3i, Q3j;
  - Role Physical (raw score) – Sum of Q4a, Q4b, Q4c, Q4d;
  - Body Pain (raw score) – Sum of Q7, Q8;
  - General Health (raw score) – Sum of Q1, Q11a, Q11b, Q11c, Q11d;
  - Vitality (raw score) – Sum of Q9a, Q9e, Q9g, Q9i;
  - Social Functioning (raw score) – Sum of Q6, Q10;
  - Role-Emotional (raw score) – Sum of Q5a, Q5b, Q5c;
  - Mental Health (raw score) – Sum of Q9b, Q9c, Q9d, Q9f, Q9h;
  - Based on SF-36 standardized scores, two summary scores are estimated: the Physical Component Score and the Mental Component Score;
- For each score estimate the 95% confidence interval will be computed.
- The IBDQ score and each of the four IBDQ domains:
  - Bowel function – Sum of questions 1, 05, 09, 13, 17, 20, 22, 24, 26, 29;

[figure not shown]
- Emotional status – Sum of questions 03, 07, 11, 15, 19, 21, 23, 25, 27, 30, 31, 32;
- Systematic symptoms – Sum of questions 02, 06, 10, 14, 18;
- Social function – Sum of questions 04, 08, 12, 16, 28;

For each score estimate the 95% confidence interval will be computed.

- For each IBD (CD and UC), a descriptive statistical analysis (global and according to disease activity) for the following WPAI data will be performed:

- In brief, the WPAI questions are: 1) if currently employed, 2) hours missed due to disease, 3) hours missed other reasons, 4) hours actually worked, 5) degree disease affected productivity while working, 6) degree disease affected regular activities.
  - Percent total work productivity impairment due to IBD (TWPI) defined as the mean of subjects total percentage of work impairment associated with IBD that results from both absenteeism and presenteeism:

CCI

- Percent work time missed due to IBD (CD or UC):

CCI

- Percent impairment while working due to IBD (CD or UC):

CCI

- Percent total activity impairment due to IBD (CD or UC):

CCI

- For each IBD (CD and UC), a descriptive statistical analysis (global and according to disease activity) of health resources (the previous 3 years) will be performed for the following events: drug therapies, number and type of imaging and laboratory testing, surgeries, number, reason and duration of hospitalizations, number and type of consultations with gastroenterologists or other medical specialists and adverse events.
- A description of the health care resource costs will be presented. Costs will be reported in total and on a per patient per month basis. Costs will be obtained by multiplying resource use with relevant unit costs. Unit costs for resource items will be collected by in Brazilian reliable administrative databases or other sources:
  - UC or CD-related health care costs:

- Consumer price index (CPI)-adjusted IBD-related health care costs will be computed as total costs, medical costs, drug costs, and other costs;
- Treatment pattern costs:
  - Treatment pattern costs will be calculated as total UC or CD related health care costs, stratified by the defined treatment patterns.
- Multivariate cost models may be developed where the observation time is divided into intervals of equal length.

The longitudinal analysis will be performed for the longitudinal analysis dataset (patients with active IBD at Day 1 included in the 12 months follow-up period):

- A descriptive statistical analysis will be performed for the main socio-demographic, clinical characteristics and treatment regimen of the included patients at Day 1 (baseline) , by IBD type (CD and UC);
- The proportion of patients with active IBD after 12 months among patients who had moderately to severely active IBD at Day 1 (baseline) will be calculated. The results will be presented as percentage.

- For CD:

CCI

- For UC:

CCI

The 95% confidence interval will be calculated for each estimate

- For each type of IBD (CD or UC), a comparison of patients that remained with active disease with patients that had mild or no activity of disease, after 12 months follow-up, regarding socio-demographic, clinical and related-treatment variables of interest will be performed:
  - For qualitative variables, the assessment of a significant difference between groups will be done using the Chi-Square Test or the Fisher's Exact Test depending if the assumption of cell frequency to be made;
  - For quantitative variables, the assessment of a significant difference between groups will be made through the t-test for independent samples or Mann-Whitney test in case of non-normality of the quantitative variable distribution;
  - If applicable, for patients with CD and UC, the assessment of independent variables which can be associated with the disease control (no or mild activity) after 12 months

follow-up will be performed using a logistic regression model. The ORs estimates and the respective 95% confidence intervals will be presented.

- If applicable, a survival analysis, with Kaplan Meier curves and Cox regression models to identify factors associated with the time of achieving mild or no activity with baseline treatment (continued or initiated at baseline) (dependent variable) will be performed for each type of IBD. The event of interest will be: have mild activity or no active disease. Thus, patients who remained with active disease or who change treatment due to lack of disease control will be censored and, conversely, success will be defined as having mild or no active disease. The survival analysis will include:
  - A non-parametric estimation of the survival function using the Kaplan-Meier estimator (global and stratified by categories for each categorical variable).
  - A comparison of estimated survival function curves of the different categories in each variable using the Log-Rank non-parametric test.
  - If applicable, the semi-parametric Cox proportional hazards model will be adjusted to identify potential factors associated with the time of achieving mild or no activity with baseline treatment (continued or initiated at baseline). The hazard ratios (HR) estimates and the respective 95% confidence intervals will be presented.
- A descriptive statistical analysis will be performed for the number and reason for treatment changes, as well for treatment patterns during the 12 month follow-up period by IBD type (CD and UC);
- For each type of IBD (CD or UC), a comparison of patients with treatment changes with those without changes 12 month follow-up, regarding main socio-demographic, clinical and treatment-related variables (at baseline) will be performed
  - For qualitative variables, the assessment of a significant difference between groups will be done using the Chi-Square Test or the Fisher's Exact Test depending if the assumption of cell frequency to be made;
  - For quantitative variables, the assessment of a significant difference between groups will be made through the t-test for independent samples or Mann-Whitney test in case of non-normality of the quantitative variable distribution;
  - If applicable, Poisson regression models based on generalized linear equations will be adjusted to investigate the relationship between variables of interest and the incidence of the treatment changes during follow-up. The incidence rate ratios (IRRs) estimates and the respective 95% confidence intervals will be presented.

## 7.7 Missing data

Missing values will not be replaced in this study.

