The Inflammatory Bowel Disease Questionnaire (IBDQ) is a 32-item questionnaire that measures 4 dimensions: bowel function, emotional status, systemic symptoms, and social function. Within dimensions, each question presents seven possible answers/points. The score for each dimension results from the sum of points. Hence, the total score ranges from 32 to 224, with higher scores representing better quality of life (34). A Portuguese (Brazil) version was already validated (35). The IBDQ is not validated for patients with ostomies and therefore should not be applied for these patients. For more information, please consult <http://www.flintbox.com/public/project/641>.

The Work Productivity and Activity Impairment questionnaire (WPAI) assesses the impact of IBD on work productivity and daily activities during the previous 7 days. In brief, the WPAI questions are: 1) if currently employed, 2) hours missed due to disease, 3) hours missed other reasons, 4) hours actually worked, 5) degree disease affected productivity while working, 6) degree disease affected regular activities (7). WPAI generates four component scores: percentage of work time missed (absenteeism); percentage of impairment while working (presenteeism); percentage of overall work impairment (absenteeism and presenteeism combined); and percentage of activity impairment. Unemployed patients only answer to questions related to employment status and activity impairment. Scores for WPAI range from 0% ('no impairment') to 100% ('total loss of work productivity/activity'). For more information, please consult http://www.reillyassociates.net/WPAI_General.html.

Treatment

- Previous treatments or regimens (aminosalicylates, steroids, immunomodulators, immunosuppressors, biologics, probiotics, antibiotics); start date; end date, dose, reason for discontinuation;
- Treatment started at Day 1 (name, dose);
- Previous surgeries for IBD.

At follow up appointment only:

- Therapeutic strategy: maintain current treatment vs discontinued;
- If discontinued, new treatment (name, dose, start date), and reason for discontinuation.

Other health care resources related with IBD management

- Imaging and laboratory testing;
- Surgeries;
- Hospitalizations;
- Consultations;
- Adverse Events.

8 Management and Reporting of Adverse Events

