10.5 Handling of missing data

Given that all analyses are descriptive in nature, no imputation of missing data will be performed, except when detailed in the SAP regarding the PRO tools.

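### The SAP's blanket no-replacement rule leaves the protocol's provision for missing PRO items unused, so one blank item makes an IBDQ domain or SF-36 scale, and the totals built on it, unscorable

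*SAP*

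**What the plan says.** Protocol section 10.5 rules out imputation in general but makes a conditional allowance: "no imputation of missing data will be performed, except when detailed in the SAP regarding the PRO tools". The SAP is thus the place for any rule on unanswered questionnaire items. The whole of SAP section 7.7 is one sentence: "Missing values will not be replaced in this study". It names no exception and refers to no other section. SAP section 8, which lists the analyses added to the protocol, does not mention missing items.

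The scores concerned are sums. For the IBDQ, Protocol section 7.2 says "The score for each dimension results from the sum of points", and SAP section 7.6 lists the items of each domain, for example the emotional domain as "Sum of questions 03, 07, 11, 15, 19, 21, 23, 25, 27, 30, 31, 32". For the SF-36, SAP 7.6 defines eight raw scale sums and then adds: "Based on SF-36 standardized scores, two summary scores are estimated: the Physical Component Score and the Mental Component Score". Protocol 7.2 makes clear that both component scores draw on all eight scales.

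**The concern.** A sum with an unanswered term is undefined unless a scoring rule says otherwise, and 7.7 forbids filling the gap. The plan would then discard a whole domain or scale, and every summary built on it, because of a single blank, even when the patient answered everything else.

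Quality of life is a stated secondary objective. SAP sections 7.6 and 8 use these scores for means with confidence intervals, for tests by disease activity, biologic use and hospitalization, and for correlations between instruments. Protocol 10.5 justifies having no imputation by the descriptive character of the analyses. That reason does not cover the hypothesis tests that the SAP plans on these scores.

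The active-disease group, which is one side of the main comparison, is small. It can least afford to lose patients whose data are nearly complete.

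**Working it through.** **Item counts (SAP 7.6).**
- IBDQ: bowel 10, emotional 12, systemic 5, social 5. 10 + 12 + 5 + 5 = 32. With seven points per item, the total runs from 32 × 1 = 32 to 32 × 7 = 224, which reproduces the range in Protocol 7.2. That range presupposes that all 32 items are answered.
- SF-36: scales of 10, 4, 2, 5, 4, 2, 3 and 5 items. 10 + 4 + 2 + 5 + 4 + 2 + 3 + 5 = 35 items enter a scale. All 35 are needed for the Physical and Mental Component Scores.

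**Loss under 7.7 as written.** Let q be the chance that an item is blank, independently across items. A score that needs k items is lost with probability 1 − (1 − q)^k. The documents give no value for q, so a range is shown.

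| Score | k | q = 0.5% | q = 1% | q = 2% |
|---|---|---|---|---|
| Shortest SF-36 scales | 2 | 1.0% | 2.0% | 4.0% |
| IBDQ systemic or social | 5 | 2.5% | 4.9% | 9.6% |
| IBDQ bowel; longest SF-36 scale | 10 | 4.9% | 9.6% | 18.3% |
| IBDQ emotional | 12 | 5.8% | 11.4% | 21.5% |
| IBDQ total | 32 | 14.8% | 27.5% | 47.6% |
| SF-36 component scores | 35 | 16.1% | 29.7% | 50.7% |

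For example, at q = 1%: 1 − 0.99^32 = 27.5% and 1 − 0.99^35 = 29.7%. Of the planned 400 patients, that is about 110 without an IBDQ total (before ostomy patients are set aside) and 119 without component scores.

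**Effect on the activity comparison.** SAP section 6 expects inadequate control in 20% to 30%, with CD and UC split evenly. Per disease that is 0.20 × 200 = 40 to 0.30 × 200 = 60 active patients. Losing 27.5% leaves 40 × 0.725 = 29 to 60 × 0.725 = 43.5, or about 44, with an IBDQ total.

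**Loss under a half-item rule.** A scale of k items is now lost only if more than half are blank, with probability P(Binomial(k, q) > k/2). At q = 1% the three-item SF-36 scale gives 3 × 0.01² × 0.99 + 0.01³ = 0.030%, and each two-item scale gives 0.01² = 0.010%. Combined as 1 − Π(1 − p), where p is each scale's loss probability, about 0.05% of patients lose any SF-36 scale and about 0.002% any IBDQ domain. At q = 2% the figures are 0.22% and 0.016%.

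**The case against.** Several points can fairly be made for the plan.

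- *The SAP does not breach the protocol.* A reader might infer that 7.7 contradicts Protocol 10.5. It does not. The exception applies only where the SAP spells one out, and an SAP that spells out none complies. The provision has been left unused, which is a gap and not a conflict. This stands.
- *The rule may exist elsewhere.* The SAP contents list an appendix on derived variables, and its text is not available here. It may contain scoring rules. This stands as a limit on the finding. Even so, an appendix rule would sit beside an unqualified sentence in 7.7, and the two would need reconciling.
- *The large percentages apply only to the totals.* A reader might picture one 36-item sum that fails on any blank. Neither document defines such a score. One blank SF-36 item affects one scale, and through it the two component scores, while the other seven scales survive. At 1% the losses per scale or domain are about 2% to 11%. This stands, and the table keeps the two kinds of loss apart.
- *The blank rate and independence are assumed.* Protocol sections 9.1 and 9.4.1 provide automatic checks, queries and a validation plan for missing data, and the questionnaires are completed only once, on Day 1. These may keep the rate low, and clustering of blanks within patients would lower the share affected. This also stands, and is why a range is given.

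Two stronger readings are tempting but unsupported. First, blanks might be skipped in the sum, which would lower an IBDQ total by 1 to 7 points per blank and make patients look worse. The text does not say so, and this is only one way a programmer might read it. Second, sicker or less educated patients might skip more items. Neither document says anything about who leaves items blank.

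**Conclusion.** The point holds as a gap in the analysis plan that is cheap to close. Under SAP 7.7 as written, and without a scoring rule in the available text, one blank item removes a domain or scale and whatever is built on it. The component scores and the IBDQ total are the most exposed: roughly 15% to 16% of patients at a blank rate of 0.5%, 27.5% to 29.7% at 1%, and 48% to 51% at 2%. Individual scales and domains lose about 2% to 11% at 1%.

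These sizes rest on the assumed rate, on independence between items, and on no rule being present in the derived-variables appendix. The finding concerns avoidable data loss; no direction of bias is claimed. The primary endpoints, the proportions with active CD and UC on Day 1, do not use these questionnaires and are unaffected.

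**What to change.** Amend SAP 7.7 as follows.

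- Pro-rate an SF-36 scale or IBDQ domain from the patient's own answered items when at least half of its items are answered. Otherwise set it to missing.
- Form the IBDQ total only when all four domains are scorable, and the two SF-36 component scores only when all eight scales are.
- Keep no replacement for all other variables.
- Do not count not-applicable cases as missing: the IBDQ in ostomy patients and the WPAI work items in the unemployed.
- Report, by instrument, how many questionnaires were pro-rated and how many remained unscorable, and repeat the analyses with complete questionnaires only as a check.
- If the derived-variables appendix already holds a scoring rule, reconcile 7.7 with it and add a cross-reference.

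The cost is SAP wording and scoring code; no new data are needed. The downside is small: for a few items the plan assumes that a patient's other answers in the same scale stand in for the blank. That assumption is strongest in the two-item SF-36 scales, where one answer would represent both, and the complete-questionnaire check would show whether it matters.

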## 8 PROTOCOL CLARIFICATIONS/AMENDMENTS

As the amendments will not affect the data collection plan, this SAP was written in accordance with the information contained in Amendment 1 of study protocol, Version 17 Oct 2016. Since the Amendment was implemented at the end of the recruitment period at only one center and after the recruitment for the remaining centers, the section “Disposition of Subjects” will specify how many subjects were included based on the eligibility criteria described in the Amendment.

The following statistical analysis not described in the protocol should be considered:

- 1) General considerations: for each study endpoint, data will be summarized by study sites. Study sites can be classified as region: PI, BA, MG, GO, SP, PR, RS and RJ (Figure 2). The study sites/region should be considered as independent variable to be included in the regression models for the comparison of patients with no or mild activity with patients with disease activity.

[figure not shown]

Figure 2 – Study sites by region.

- 2) Subject's disposition: The study deposition should also be presented by IBD type and regions.
- 3) Demographic and other characteristics: The descriptive statistical analysis should also be performed by regions.
- 4) Primary Analysis: The proportion of patients with moderate to severe CD or UC should be calculated and compared by regions.
- 5) Secondary Analysis: For cross-sectional analysis dataset the descriptive statistical analysis will be performed also by region. The multivariate logistic regression model should include as independent variables all variables with  $p < 0.020$  in bivariate analysis. Optimized model present only variables with statistical significant OR (Odds Ratio). The region should be included as independent variable. For longitudinal analysis dataset the proportion of patients with moderate to severe CD or UC after 12 month follow-up should be calculated and compared by region. As for cross-sectional analysis dataset, the multivariate logistic

regression model should include as independent variables all variables with  $p < 0.020$  in bivariate analysis. Optimized model present only variables with statistical significant OR (Odds Ratio). The region should be included as independent variable.

For cross-sectional analysis dataset, the comparison of SF-36 scale scores or component summary scores, EQ-5D VAS scale and IBDQ domain scores or total score according to disease activity will be performed through the t-test for independent samples or Mann-Whitney test in case of non-normality of the quantitative variable distribution. The association between each EQ-5D dimension and disease activity will be determined for each IBD type using Chi-Square Test. If applicable, if the number of patients in the levels of each dimension is small, the severity of each dimension will correspond to: have problems (group moderate, severe and unable/extreme problems) and have no problems (group slight or no problems). The correlation of scales scores of IBDQ and EQ-5D dimensions or VAS scale with SF-36 scales scores will be determined for each IBD type using Pearson or non-parametric Spearman's correlation coefficient.

Also for cross-sectional dataset, patients with moderate to severe disease will be compared with patients with no or mild disease regarding WPAI data (percent total work productivity impairment due to IBD, percent work time missed due to IBD, percent impairment while working due to IBD and percent total activity impairment due to IBD) through the t-test for independent samples or Mann-Whitney test in case of non-normality of the quantitative variable distribution.

- 6) Other analysis: The influence of demographic characteristics, comorbidities and extra-intestinal manifestations on the quality of life will be assessed. For each type of IBD, a comparison of patients using biologic treatment and patients who not use biologic treatment regarding quality of life data will be done. Same analysis will be performed for patients who were hospitalized and patients who were not hospitalized.  
IBD treatment-related procedures in the previous 3 years will be described for patients using biologic treatment and patients who not use biologic treatment.

Note: Regions variable should be considered as independent variable for the regression analysis.

- 7) Longitudinal analysis: A sensitivity analysis will be performed to determine the proportion of patients with active IBD after 12 months, among patients who had moderately to severely active IBD at Day 1 (baseline), considering the CDAI/ HBI (for CD patient) or Mayo (for UC patients) scores collected during the IBD specialist appointments, allowing a time window of 1 month (30 days) to assess disease activity ( $M12 = (Day1 + 365 \text{ days})$  or  $(Day1 + 365 \text{ days}) - (30 - 1 \text{ days})$ ). The results will be presented as percentage and the 95% confidence interval will be calculated.

